### **5.5.5 Permitted dose adjustments and interruptions of study treatment**

The dose can be adjusted in a range up to, but not exceeding 18 mg/day as appropriate depending on the clinical conditions until the dose reaches the maintenance dose.

In the event of gastrointestinal disorders (e.g. nausea, vomiting) and other tolerability problems, the dose should be reduced or treatment should be temporarily interrupted until these adverse effects resolve. The following treatment adjustments should be applied, and the actions to be taken in the event of consecutive days of interruption are described in detail in [Table 5-3](#).

**Table 5-3 Actions following dose interruption**

| Consecutive days missed | Actions when patients with 9 mg/day patch  |
|-------------------------|--|
| ≤ 4 days                | Can be resumed at the same dose (9 mg/day), and the dose at resumption should be maintained for a minimum of 2 week after treatment resumption. If the dose is shown to be well-tolerated, the dose can be increased to 18 mg/day. |
| ≥ 5 days - ≤ 28 days    | Treatment should be resumed at the initial starting dose (9 mg/day), and follow for 1 step titration method to reach the maintenance dose of 18 mg/day.  |

| Consecutive days missed | Actions when patients with 9 mg/day patch   |
|-------------------------|---|
|                         | 
Patients who still have tolerability issues with 9 mg/day, consider to resume the treatment at the initial starting dose (4.5 mg/day)
 
When resumed at the initial dose of 4.5 mg/day, follow for 3 step titration method.
 
After treatment resumption, the dose at resumption should be maintained for a minimum of 2 weeks. If the dose is shown to be well-tolerated, the dose can be increased to the pre-resumption dose at intervals of 2 weeks or more.
   |
| >28 days                | Must discontinue study drug administration.   |
| Consecutive days missed | Actions when patients with 18 mg/day patch  |
| ≤ 4 days                | Can be resumed at the same dose, 18 mg/day  |
| ≥ 5 days - ≤ 28 days    | 
Treatment should be resumed at the initial starting dose (9 mg/day) and follow for 1 step titration method to reach the maintenance dose of 18 mg/day.
 
In case of patients showing some tolerability issue with 9 mg/day at this time, repeat same procedure with 9 mg/day described above
 
When resumed at the initial dose of 4.5 mg/day, follow for 3 step titration method.
 
After treatment resumption, the dose at resumption should be maintained for a minimum of 2 weeks. If the dose is shown to be well-tolerated, the dose can be increased to the pre-resumption dose at intervals of 2 weeks or more.
 |
| >28 days                | Must discontinue study drug administration.   |

These changes must be recorded on the Dosage Administration Record CRF (eCRF).

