| Study drug/ treatment                           | Any single drug or combination of drugs administered to the patient as part of the required study procedures; includes investigational drug (s), active drug run-ins or background therapy  |
| Study/investigational treatment discontinuation | Point/time when patient permanently stops taking study/investigational treatment for any reason; may or may not also be the point/time of premature patient withdrawal  |
| Subject Number                                  | A number assigned to each patient who enrolls into the study  |
| Variable  | A measured value or assessed response that is determined in specific assessments and used in data analysis to evaluate the drug being tested in the study   |
| 1-step titration                                | 1-step titration begins treatment with a rivastigmine patch 9 mg/day for 4 weeks, followed by a dose increase to 18 mg/day.   |

## Amendment 1

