## 2. Titration phase [8 weeks: week 1 (Day 1) to week 8 (Day 56)].

On the same day or next day (Day 1) following baseline visit, patients will begin treatment with a rivastigmine patch 9.0 mg/day and will be up-titrated after 4 weeks to reach the maintenance dose of 18 mg/day. Should tolerability problems occur, the investigators can decide to interrupt the treatment temporarily or to reduce the dose (see [Section 5.5.5](#)). The highest well-tolerated dose for each individual patient should be established within the titration period. The investigators also can use their clinical judgement to switch those patients to slower 3-step titration scheme in order to reach the maintenance dose of 18 mg/day or find the highest well-tolerated dose for each individual patient. Those patients will be allowed to stay in the study. During the titration period, visits will take place every 4 weeks.

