**Table 5-1 Dosage form and drug content for 1 step titration**

| Form                            | Loading dose / Content per one patch | Size               |
|---------------------------------|--------------------------------------|--------------------|
| Exelon ® patch 9 mg  | 9 mg rivastigmine                    | 5 cm   |
| Exelon ® patch 18 mg | 18 mg rivastigmine                   | 10 cm  |

If patients cannot tolerate 1-step titration method to reach the maintenance patch dose of 18 mg/day, the investigators can use their clinical judgement to switch those patients to slower 3-step titration method in order to reach the maintenance dose of 18 mg/day or find the highest well-tolerated dose for each individual patient. Once the dose started at 4.5 mg of rivastigmine once a day, as a general rule, the dose should be increased to 4.5 mg a day at 4-week intervals to 18 mg once a day. Those patients will be allowed to stay in the study. Patients with doses below the planned dose will continue to participate in the study.

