#### **Titration Period (Week 1 to 8)**

The day or following day (in case of a patient who takes his/her previous oral ChE inhibitors at the baseline visit) of the baseline visit (Day 1), all patients will start study treatment with one rivastigmine patch of 9 mg once a day. During the titration period, as a general rule, the dose should be increased to 18 mg once a day at 4 weeks later:

Week 1 – 4: Rivastigmine patch 9 mg/day

Week 5 – 8: Rivastigmine patch 18 mg/day

Should tolerability problems occur during the titration period, the dose can be adjusted in a range not exceeding 18 mg a day as appropriate depending on the clinical symptoms until the dose reaches the maintenance dose. In the event of gastrointestinal disorders (e.g., nausea, vomiting) or other tolerability problems, the dose should be reduced or treatment should be

temporarily interrupted until these adverse effects resolve. Patch treatment can be resumed at the same dose or previous well tolerated dose if interruption of treatment is around or within 4 days. Otherwise, treatment should be resumed at the initial starting dose (e.g. 4.5 mg or 9 mg). After treatment resumption, the dose at resumption should be maintained for a minimum of 2 weeks. If the dose is shown to be well-tolerated, the dose can be increased to the pre-resumption dose at intervals of 2 weeks or more.

Rivastigmine patch dose adjustments required for tolerability problems will be according to the dose adjustment scheme defines in [Section 5.5.5](#).

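### Table 5-3 conflicts with the 4-week titration schedule: an early short interruption on 9 mg can bring 18 mg forward, and both 5-28 day cells carry a 4-week and a 2-week interval

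*Protocol*

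**What the plan says.** **The schedule.** The protocol Glossary states: "1-step titration begins treatment with a rivastigmine patch 9 mg/day for 4 weeks, followed by a dose increase to 18 mg/day". Section 5.5.4 (Titration Period) agrees: "as a general rule, the dose should be increased to 18 mg once a day at 4 weeks later", followed by the line "Week 5 – 8: Rivastigmine patch 18 mg/day". For patients moved to the slower scheme, the text after Table 5-1 in Section 5.1.1 says "the dose should be increased to 4.5 mg a day at 4-week intervals to 18 mg once a day". Section 1.1 puts the minimum time to the effective dose under that scheme at 12 weeks.

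**Table 5-3, 9 mg patch, 4 days or fewer missed.** The patient may resume 9 mg, and "the dose at resumption should be maintained for a minimum of 2 week after treatment resumption". If that is tolerated, 18 mg may follow. The row is silent on time already spent on 9 mg and on the 4 weeks.

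**Table 5-3, 5 to 28 days missed.** The 9 mg cell says: "Treatment should be resumed at the initial starting dose (9 mg/day), and follow for 1 step titration method". The 18 mg cell gives the same instruction. Both cells refer to the 3-step method if the restart is at 4.5 mg. Both then end with a two-week hold, after which "the dose can be increased to the pre-resumption dose at intervals of 2 weeks or more". Section 5.5.4 repeats this two-week rule for the titration period.

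**Reductions.** Section 5.5.4 (Maintenance Period) sends dose reductions and later increases to Section 5.5.5. That section names reduction as an option for tolerability problems, but its detailed table covers missed days only.

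**SAP.** Deviation S02 (Section 5.2, Table 1) restates the Glossary definition and carries code 1, which removes the patient from the per protocol analysis.

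**The concern.** Table 5-3 is the operative text for patients who have just had a tolerability problem. Two sites can both follow the protocol and still re-escalate such patients on different timetables. In one row, a patient who interrupted may reach the higher dose sooner than one who never did.

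Four results could then depend on which sentence a site reads:

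- **Dose at the Week 8 MMSE.** This is a secondary endpoint.
- **Per protocol membership.** A patient escalated as the short-interruption row permits has not had 4 weeks on 9 mg and, read literally, meets S02. The per protocol set feeds a supportive analysis of the primary endpoint (SAP 2.5.4) and the secondary efficacy analyses (SAP 2.6.1).
- **Adverse events by period.** Protocol Section 9.6.2 describes Weeks 1 to 4 as time on 9 mg. Early escalation puts events on 18 mg into that period. SAP 2.6.2.1 keeps the period but drops the dose description.
- **Treatment retention.** Protocol 9.6.3 and SAP 2.11.1 require 18 mg during the last 8 weeks.

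**Working it through.** Nominal study days are used, with Day 1 the first 9 mg patch and each increase made on the earliest day the text permits.

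**1. The plan's own figures.** 1-step: Day 1 + 28 = Day 29, the first day of Week 5, which agrees with Section 5.5.4. 3-step: 3 increases × 4 weeks = 12 weeks (84 days), which agrees with Section 1.1.

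**2. 9 mg, 4 days or fewer missed.** Let L be the day of the last patch and m (1 to 4) the days missed. Resumption is on Day R = L + m + 1, and 18 mg is permitted from Day R + 14.

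- Days 3 and 4 missed: R = 5, so 18 mg from Day 19. Time on 9 mg is 2 + 14 = 16 days, against 28 without interruption.
- Earliest case, Day 2 missed: R = 3, so 18 mg from Day 17, which is 29 − 17 = 12 days ahead of schedule, after 1 + 14 = 15 days on 9 mg.
- Limit: R + 14 < 29 requires R ≤ 14. R = 15 ties at Day 29, and later resumption gives a later increase.
- If the uninterrupted patient is instead raised on the first day of the Visit 3 window (Day 21), the interrupted patient is still earlier when R ≤ 6.

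**3. 9 mg, 5 to 28 days missed.** The earliest restart is Day 7 (Days 2 to 6 missed). The 1-step method then gives 18 mg from Day 7 + 28 = Day 35, so nothing is brought forward. The pre-resumption dose is 9 mg, so the two intervals clash only on the step from 4.5 to 9 mg: 14 or 28 days.

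**4. 18 mg, 5 to 28 days missed.**

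| Restart dose | 2-week interval | 4-week method |
|---|---|---|
| 9 mg, back to 18 mg | 14 days | 28 days |
| 4.5 mg, back to 18 mg (3 steps) | 3 × 14 = 42 days | 3 × 28 = 84 days |

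Example: 18 mg on Days 29 and 30, Days 31 to 35 missed, 9 mg from Day 36. The patient is back on 18 mg from Day 36 + 14 = Day 50 or Day 36 + 28 = Day 64. An MMSE on Day 56 is taken on 18 mg under one reading and on 9 mg under the other. The same holds from Day 50 to Day 63, which is all but the first day of the Visit 4 window (Days 49 to 63).

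**5. Retention.** The last 8 weeks are Days 168 − 56 + 1 = 113 to 168. To be on 18 mg by Day 113, a restart at 9 mg must come by Day 113 − 14 = 99 or 113 − 28 = 85. A restart at 4.5 mg must come by Day 113 − 42 = 71 or 113 − 84 = 29.

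**The case against.** The strongest reply is that the texts can be read together. The 2 weeks is a minimum, the 4 weeks is stated as a general rule, and the table says the dose can, not must, be raised. In the 5-28 day cells the named method could give the sequence of doses and the last sentence the minimum spacing on return to a dose already worn. A site that always waits 4 weeks breaks neither text. All of that is fair, but the protocol does not say it, and it does not make another site's 2-week increase wrong. Nor does it rescue the short-interruption row, where 18 mg is a new dose.

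Visits are 4 weeks apart during titration, so an increase on Day 19 would need an off-schedule prescription. That makes the case less likely but does not forbid it.

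S02 may be meant only for patients who leave the 1-step scheme, since SAP 2.1.1.1 excludes those who cannot tolerate it from the per protocol analysis. The entry does not say so.

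Some stronger readings are tempting but not supported:

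- **Interruption in general speeds escalation.** Only the short-interruption 9 mg row does this, and only for resumption by Day 14.
- **4.5 mg may go straight to 18 mg.** The cells refer to the 3-step method and speak of intervals in the plural.
- **The 3-step wording in Section 5.1.1 sets a different schedule.** It says the dose rises to, rather than by, 4.5 mg. That is a slip: Section 1.1 and Table 5-2 make the sequence clear.
- **The slower scheme contradicts the 8-week titration phase.** Section 3.1 does say "The highest well-tolerated dose for each individual patient should be established within the titration period", but its maintenance-phase text allows later increases towards 18 mg.
- **Section 5.5.5 ignores reductions.** It mentions them; what it lacks is a step scheme for them.

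**Conclusion.** The conflict is real and limited to two places. In the row for 9 mg with 4 days or fewer missed, 18 mg is permitted up to 12 days ahead of schedule when treatment resumes by Day 14. In both 5-28 day cells two intervals stand together with no sentence saying which governs, and the readings differ by a factor of two.

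A reader might infer that the primary result is compromised. It is not. SAP 2.5.1 includes all patients in the full analysis set whatever their regimen, the study has one arm, and p-values are descriptive. Dose changes are recorded and doses administered are listed, so the paths taken can be described. What can shift is per protocol membership, the dose at the Week 8 MMSE, the dose worn during Weeks 1 to 4, and retention. For retention, the Day 29 limit reflects the length of the 3-step scheme itself; the conflict adds the 42-day gap between the two limits.

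The documents give no interruption rate, so the number of patients affected is unknown. The day counts assume nominal days and the earliest permitted increase, and the per protocol consequence assumes that S02 is applied as written. This warrants correction because it is a contradiction in the dosing table, but the trial's main conclusion does not depend on it.

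**What to change.** Reconcile the Glossary, the text after Table 5-1 in Section 5.1.1, both period texts in Section 5.5.4, Section 5.5.5 with Table 5-3, and SAP deviation S02, so that:

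- each Table 5-3 cell carries one interval and one target dose;
- the table states whether time on 9 mg before an interruption counts;
- the reference from Section 5.5.4 to Section 5.5.5 for reductions and later increases leads to text that covers them;
- S02 does not code as a deviation a patient treated as Table 5-3 permits.

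Which interval and dose apply, including after a reduction, is for the sponsor's clinical team.

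The cost is a protocol amendment or clarification, a letter to sites and matching SAP text. No extra patients, visits or assessments are needed. Patients already re-escalated under another reading should be described as such.

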### **5.5.6      Rescue medication**

Not applicable.

### **5.5.7      Concomitant medication**

The investigator should instruct the patient to notify the study site about any new medications he/she takes after the patient was enrolled into the study. All medications, procedures and significant non-drug therapies (including physical therapy and blood transfusions) administered after the patient was enrolled into the study must be recorded.

### **5.5.8      Prohibited medication**

The following medications are prohibited or restricted during specified periods (topical and ophthalmic formulations of the mentioned drugs below are allowed):

#### **Prohibited concomitant medications**

Use of the following treatments is NOT allowed after the start of study drug (Day 1):

1. Any investigational drug (including topical and ophthalmic investigational drugs).

2. Donepezil, galantamine.
3. Selegiline.
4. Centrally acting anticholinergic drugs.
5. Olanzapine.
6. Tricyclic and tetracyclic antidepressants.
7. Succinylcholine-type muscle relaxants.
8. Lithium.

### **Restricted concomitant medications / non-drug therapies**

The following medications / non-drug therapies are permitted, but with some limitations:

1. Initiation of the following concomitant medications should be avoided during the 4 weeks prior to efficacy assessment at baseline to Visit 8/discontinuation. Patients who have been on a stable dose of these drugs during the 4 weeks or more prior to efficacy assessment at baseline should continue on the dose without changing the dosage and administration:
  - Memantine
  - Yokukan-san
  - Yokukansankachimpihange
  - Agents which improve cerebral circulation/metabolism
  - Vitamin E- Estrogens
2. Initiation of the following concomitant medications should be avoided during the 2 weeks prior to efficacy assessment at Visit 8 if possible. Patients who have been on a stable dose of these drugs during the 4 weeks or more prior to efficacy assessment at baseline should continue on the dose without changing the dosage and administration:
  - Psychotropic medication
  - Antidepressants (tricyclic and tetracyclic antidepressants are prohibited)
  - Anxiolytics (except benzodiazepine-type hypnotics)
  - Antiepileptics
  - Drugs for Parkinson's disease
  - Hypnotics:
3. A new treatment should be limited to the following medications, but the treatment should be at the lowest effective dose and shortest duration possible. Accumulated duration must be 14 days or less during each visit.
  - Psychotropic medication: tiapride hydrochloride
  - Antidepressants : trazodone hydrochloride
  - Nonbenzodiazepine hypnotic of short duration : zolpidem tartrate zopiclone and eszopiclone . Additionally new initiation of treatment and irregular treatment such as on-demand use are prohibited during the 24 hours prior to efficacy assessment at Visit 2, 4, and 8.
4. The following drugs are allowed to use, but not recommended to use.
  - Benzodiazepine anxiolytic (Newly initiation of treatment is prohibited during the previous 24 hours prior to efficacy assessment at Visit 2, 4, and 8): rilmazafone hydrochloride, brotizolam , lormetazepam, triazolam.

5. The following new medication for atypical psychotropic must not be started after starting the study drug (Day1)
  - Risperidone, quetiapine fumarate, perospirone hydrochloride
6. Peripheral anticholinergic agents:  
Patients who have been on a stable dose of these drugs during the 4 weeks or more prior to efficacy assessment at baseline should continue on the dose without changing the dosage and administration. When new-onset urinary urgency or urinary incontinence during the study constitutes an intolerable symptom that cannot be overcome by non-pharmacological measures, initiation of treatment with peripheral anticholinergics such as oxybutynin hydrochloride, propiverine hydrochloride, tolterodine tartrate solifenacin and imidafenacin are permitted.
7. Antitussive agents, cold medicine or antihistamic antiallergy agents:  
As a rule, these agents are prohibited 1 week prior to efficacy assessment at baseline and Visit 8.
8. Rehabilitation, day care and day service:  
Any rehabilitation day care and day service during 4 weeks or more prior to efficacy assessment at baseline must not be changed significantly with content and frequency (new start / discontinuation).
9. Short stay (hospital / nursing home):  
Short stay should be limited during the previous 2 weeks prior to efficacy assessment at baseline and Visit 8.

### **5.5.9 Emergency breaking of assigned treatment code**

Emergency breaking is not applicable as this is an open-label study.

## **5.6 Study Completion and Discontinuation**

### **5.6.1 Study completion and post-study treatment**

At a minimum, caregivers of the patients who complete this study or discontinue the drug, including those who refuse to return for a final visit, will confirm the onset (or no onset) of a SAE during at least 30 days following the last dose of study drug or at the patient's last visit, and the result should be recorded in the source document & in eCRF.

### **5.6.2 Discontinuation of Study Treatment**

The drug must be discontinued for a given patient if the investigator determines that continuing it would result in a significant safety risk for that patient. The following circumstances require drug discontinuation:

1. Where an adverse event has occurred that, in the judgment of the investigator, warrants discontinuation of treatment;
2. Where an abnormal laboratory value has been found that, in the judgment of the investigator, warrants discontinuation of treatment;
3. Where aggravation of the condition has occurred that, in the judgment of the investigator, warrants discontinuation of treatment;

4. Where necessary observation and examination after the initiation of treatment has become impossible for the patient's or his/her caregiver's personal reasons;
5. Where any important deviation from the protocol has become clear;

In addition to these requirements for drug discontinuation, the investigator should discontinue the drug for a given patient if, on balance, he/she thinks that continuation would be detrimental to the patient's well-being.

The investigator should record the last known date a patient takes the drug and select primary reason for premature discontinuation from the following reasons on the study completion page in eCRF.

1. Adverse Event(s)
2. Abnormal lab value(s)
3. Abnormal test procedure result(s)
4. Unsatisfactory therapeutic effect
5. Subject's condition no longer requires study
6. Protocol deviation
7. Subject withdrew consent
8. Lost to follow-up
9. Administrative problem
10. Death

Patients who discontinue the drug should NOT be considered withdrawn from the study. See [Section 6](#) for the required assessments of these patients after discontinuation of the treatment.

### **5.6.3 Withdrawal of informed consent**

Patients/subjects may voluntarily withdraw consent to participate in the study for any reason at any time. Withdrawal of consent from the study is defined as when a patient:

- Does not want to participate in the study anymore  
and
- Does not want any further visits or assessments  
and
- Does not want any further study related contacts  
and
- Does not allow analysis of already obtained biologic material

In this situation, the investigator must make every effort (e.g. telephone, e-mail, letter) to determine the primary reason for the patient's decision to withdraw his/her consent and record this information on medical chart.

The drug must be discontinued and no further assessments conducted, and the data that would have been collected at subsequent visits will be considered missing.

Further attempts to contact the patient are not allowed unless safety findings require communicating or follow-up.

All efforts should be made to complete the assessments prior to study withdrawal.

Patients who are prematurely withdrawn from the study will not be replaced by an equal number of newly enrolled patients.

